Short-term effects of untreated procedural pain in infancy and early childhood include delayed wound healing, changes in immune system function, endocrine and biochemical changes, increased cortisol and catecholamine release, increased glucagon, growth hormone, aldosterone, renin, and antidiuretic hormone levels, and decreased insulin secretion. In addition, physiological changes such as apnea, bradycardia, tachycardia, skin color changes, hypertension, sweating of the palms, increased intracranial pressure, respiratory rate, and muscle tone, as well as behavioral changes and crying, are also present (7). It is also noted that it causes long-term sequelae, including anticipatory anxiety (8). These effects include decreased analgesic efficacy, increased sensitivity to pain and needle phobia, avoidance of routine health care checkups, and a tendency not to comply with medical treatment and preventive measures (6).

From birth and throughout infancy, they are routinely exposed to painful procedures as part of routine preventive care (15). Depending on their stage of development, they may lack the communication skills and cognitive development necessary to describe the nature, location, severity, or intensity of their pain. It is a complex, multidimensional, and subjective condition that can be difficult to assess and manage, especially in infants and young children (16).

However, ensuring a thorough assessment of their physiological status during painful procedures and developing evidence-based, appropriate pain control strategies with an understanding of the effects of pediatric pain is both a medical and ethical responsibility for pediatric nurses (1, 17). The World Health Organization (WHO) estimates that 12 billion It is estimated that injections are administered, with approximately 5% of these being childhood vaccinations (6). Pain associated with vaccination is considered a significant adverse event following vaccination and therefore pain management should be part of every vaccination (9).

To minimize these adverse events, the American Academy of Pediatrics and the International Neuropsychiatric Pain Group recommend reducing pain in infants and using non-pharmacological pain relief methods as the primary option in newborns (18, 19). Studies indicate that non-pharmacological tactile stimuli such as vibration may have the potential to reduce pain due to the presence of numerous large fibers in the skin (11, 20-22). Infants are exposed to mechanical vibration through vibrating infant seats or swings to calm them in both hospital and home settings (23). However, it is known that vibration applied with a mechanical hand vibrator is also used as a method of chest physiotherapy in Neonatal Intensive Care Units (NICUs) to calm colicky infants (24, 25).

It has been suggested that manipulations such as rubbing, applying pressure, and tapping directly on or below painful areas may also alleviate pain by releasing beta-endorphins into the bloodstream (13). It has been suggested that simple manual pressure applied to the injection site (similar in effect to the fiske method) may be a useful technique for reducing injection pain (7, 13, 26). The current literature shows that non-pharmacological mechanical vibration and fiske applications may be effective in reducing injection pain (7, 11).

Based on this information, the aim is to evaluate the effect of mechanical vibration and fiske tapping methods in reducing pain during vaccination in one-month-old infants receiving healthcare as part of routine primary preventive healthcare services.

Aim

This study aims to investigate the effect of tapping the injection site prior to the second dose of Hepatitis B vaccine administered to the anterior surface of the vastus lateralis muscle during infancy and the application of mechanical vibration to the injection site throughout the vaccination procedure on acute pain, crying duration, and physiological parameters that may occur due to intramuscular injection.

Research Hypotheses

Main Hypotheses

Hypothesis 0a (H0a): There is no difference in pain between the control group and the study groups when mechanical vibration is applied during Hepatitis B vaccination in infants compared to routine Hepatitis B vaccination.

Hypothesis 1a (H1a): There is a difference in pain between the control group and the study groups when mechanical vibration is applied during Hepatitis B vaccination in infants compared to routine Hepatitis B vaccination.

Hypothesis 0b (H0b): There is no difference in pain between the control group and the study groups when comparing the routine Hepatitis B vaccination with the tap method applied during Hepatitis B vaccination in infants.

Hypothesis 1b (H1b): There is a difference in pain between the control group and the study groups in infants during routine Hepatitis B vaccination and during Hepatitis B vaccination administered using the finger-prick method.

Method

Type of Research

The research is planned to be conducted as a randomized controlled trial to examine the analgesic and physiological effects of mechanical vibration and fiske methods in infant vaccinations.

Location and Timing of the Research

Research data will be collected at Gümüşhane Kelkit No. 1 ASM. According to the study schedule, ethical committee and institutional approval will be obtained before starting the research, following the submission and acceptance of the thesis proposal, and then the data collection process will begin. Data collection, obtaining expert opinions, and data entry will take place over a 12-month period. Data analysis and thesis report writing will be completed within a three-month period, and the research is expected to be carried out according to the planned schedule.

Ethical Aspects of the Study

Before starting the study, the necessary permissions will be obtained from the Scientific Research Ethics Committee of Karadeniz Technical University Health Sciences. After obtaining permission from the ethics committee, institutional permission will be obtained from the Gümüşhane Provincial Health Directorate, to which Gümüşhane Kelkit No. 1 ASM is affiliated, in order to carry out the study. All parents of newborn babies included in the study will be informed about the purpose, type, implementation process, and content of the study, the purpose for which the video images taken during the data collection process will be used, the fact that all data will be stored on the researcher's personal computer, and where the obtained data will be used. Verbal and written consent will be obtained from the parents.

Study Population and Sample

The study population will include infants whose mothers, who agreed to participate in the study, applied for the second dose of the Hepatitis B vaccine at the end of the first month as part of routine preventive care at Gümüşhane Kelkit No. 1 ASM and who met the inclusion criteria for the study.

A power analysis was performed to select the patients to be sampled. The G*Power 3.1.9 program was used to calculate the number of participants to be included in the study. During the calculation, the effect size was taken as 0.31 based on Kanbur's (2021) study for the parameters specified according to the type of test, the margin of error was taken as 0.05, the power value was taken as 0.80, the number of groups was taken as 3, and the number of measurements was taken as 3. The calculation resulted in a minimum participant number of 72. Accordingly, it was planned to include a minimum of 24 participants in each group (27).

Research Inclusion Criteria

The parent agrees to participate in the study/volunteers to participate,

The gestational age is between 38 and 42 weeks,

The birth weight is between 2500 g and 4000 g,

No pain medication is administered prior to vaccination,

Body temperature is within normal limits,

Exclusion Criteria

Parents who do not consent to participate in the study,

Gestational age below 38 weeks or above 42 weeks,

Infants with congenital diseases or birth defects will not be included in the study.

Data Collection Tools

Newborn Baby Identification Form

The newborn infant information form created by the researcher consists of a total of nine questions, including the infant's group number, gender, gestational age, mode of delivery, birth weight and length at birth, postnatal age, current weight and height, and feeding method (27, 29).

Parent Information Form

The parent information form created by the researcher consists of a total of six questions, including the parent's group number, mother and father's ages, education status, and occupation information (27).

Newborn Baby Observation Form

The observation form prepared by the researcher is a form on which physiological parameters will be recorded, including the baby's group, crying time with the start of the vaccination procedure, the baby's body temperature before and after the procedure, the baby's respiratory rate before and after the procedure, and oxygen saturation and heart rate before, during, and after the procedure. This information about the infant before, during, and after the procedure **will be observed by the researcher and recorded on this form (27, 29).**

Neonatal Infant Pain Scale (NIPS)

Developed by Lawrence and colleagues, it is used to measure the behavioral responses to pain in preterm and term infants during the first six weeks after birth. The scale ensures that the infant's behavior, which is the first step in meeting the newborn's needs, is objectively assessed at the bedside. The scale's reliability coefficient has been found to be between 0.92 and 0.97. It is stated that the scale can be used reliably and can measure the effectiveness of the intervention, and six behaviors in response to pain are evaluated (27). Facial expression, breathing pattern, arm movements, leg movements, and alertness are scored as 0 or 1, while crying is scored as 0, 1, or 2. The total score ranges from 0 to 7, with a high score indicating severe pain. The Turkish adaptation of the scale was performed by Akdovan and Çiğdem in 1999 (28).

Application Tools

Mechanical Vibrator

The Norco NC70209 brand mini vibration device, which is lightweight, portable, and battery-operated, with silicone heads for small areas, vibrates at 5500 rpm and is intended for use on infants in the mechanical vibration group.

Video Camera

The digital camera of the Samsung Galaxy M31 phone is planned to be used to determine pain levels before, during, and after the Hepatitis B vaccination procedure in infants, to evaluate physiological parameters, to accurately calculate crying times, and to check for inter-observer agreement in the evaluation of pain scores. The camera has an 8-megapixel video resolution and features that allow images to be reviewed on a wide screen.

Pulse Oximeter

An ACCURATE handheld rechargeable pulse oximeter device is planned to be used at the patient's bedside to easily view measurement trends on the screen for determining oxygen saturation and heart rate in infants. The device is designed to monitor pulse and blood oxygen levels in premature infants, newborns, children, and adults. Values can be tracked by attaching it to the adjustable wrist, ankle, or finger.

Thermometer

A KANGJI brand, model GQ-129, non-contact infrared digital screen thermometer is planned to be used to measure the body temperature of infants. Body temperature measurement will be taken from the forehead, and the thermometer will be held 3-5 cm away from the infant's forehead.

Data Analysis

IBM SPSS 27 software will be used to analyze the data in this study. Continuous data will be presented as mean \pm standard deviation, while categorical data will be presented as frequency and percentage. If the values obtained from the measurements taken for each variable throughout the study show a normal distribution, the parametric test ANOVA test will be used to compare repeated measurement results. If the values do not show a normal distribution, the non-parametric Friedman test will be used. For intergroup analyses, the parametric test, one-way ANOVA, will be used for those showing a normal distribution, and the non-parametric test, Kruskal Wallis H test, will be used for those not showing a normal distribution. Statistical significance will be accepted as $p < 0.05$ for all analyses.

Research

1. Güven SD, Çakırer Çalbayram N (2023). The effect of Helper skin tap technique on hepatitis B vaccine intramuscular injection pain in neonates: A randomized controlled trial. *Explore* 19(2): 238-242.

4. Türk Dil Kurumu (2023). Türk Dil Kurumu Sözlükleri [online]. Erişim adresi: <https://sozluk.gov.tr/>. [Erişim tarihi: 15.12.2023].

6. Cwynar CM Osborne K (2019). Immunization-Associated Pain: Taking Research to the Bedside. *Journal of Pediatric Health Care* 33(4): 446-454.

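### The 0.80 power claimed for 72 infants relies on three measurements per infant; the planned one-way ANOVA on one value per infant has about 0.63 if f = 0.31

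*Combined protocol and SAP*

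**What the plan says.** All references are to the combined protocol and SAP.

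- **Study Population and Sample.** The calculation uses an effect size of 0.31 from a cited doctoral thesis, and "the margin of error was taken as 0.05". It continues: "the power value was taken as 0.80, the number of groups was taken as 3, and the number of measurements was taken as 3". The outcome is: "The calculation resulted in a minimum participant number of 72", or at least 24 per group. Neither the G*Power procedure nor the correlation between measurements is named. The text does not say whether 0.31 is Cohen's f, or for which effect.
- **Data Analysis, between groups.** "For intergroup analyses, the parametric test, one-way ANOVA, will be used for those showing a normal distribution", with Kruskal-Wallis otherwise.
- **Data Analysis, over time.** If the data are normal, "the parametric test ANOVA test will be used to compare repeated measurement results". The alternative is: "If the values do not show a normal distribution, the non-parametric Friedman test will be used".
- **Application Tools, Video Camera.** The recording serves "to determine pain levels before, during, and after the Hepatitis B vaccination procedure in infants", which are presumably the three measurements in the power calculation.
- **Research Hypotheses.** Both main hypotheses concern a difference in pain between the control and intervention groups.

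**The concern.** The hypotheses are between-group, so the test that answers them is the one listed for intergroup analyses. A one-way ANOVA or Kruskal-Wallis test uses one value per infant. The plan describes no averaging over the three times, so the natural reading is a test at one time point. The power calculation credits the trial with three measurements per infant, and the planned test cannot use that information.

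The stated power is the only justification given for 72 infants. If the true power at a time point is well below 0.80, a non-significant result for vibration or tapping will be taken as stronger evidence of no effect than it is. Several looks do not repair this, because no primary time point is named and every analysis is judged at p < 0.05.

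**Working it through.** **Inputs from the plan:** effect size 0.31 (read as Cohen's f), alpha 0.05, target power 0.80, 3 groups, m = 3 measurements, N = 72.

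**Assumptions, because the plan is silent:** f = 0.31 applies to a single measurement; the correlation rho between measurements is as shown. Power is from the noncentral F distribution, with N in multiples of 3.

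**1. Reproducing 72.** Repeated-measures ANOVA, between factors: lambda = N·f²·m / (1 + (m − 1)·rho), df = 2 and N − 3.
- rho = 0.5, N = 72: lambda = 72 × 0.0961 × 3 / 2 = 10.38, df 2 and 69, power **0.813**.
- rho = 0.5, N = 69: power 0.794. The minimum is therefore exactly 72.
- Minimum N at other correlations: 66 (rho 0.4), 69 (0.45), 75 (0.55).

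A group-by-time interaction calculation can also return 72. With lambda = f²·N·(m − 1)·eps and df = 4·eps and 2(N − 3)·eps, eps = 1 gives 66. With eps = 0.9, N = 72 gives lambda = 12.45 and power 0.818. The between-factors route is thus likely but not certain. Both routes use three measurements per infant.

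**2. The planned test.** One-way ANOVA at one time point: lambda = N·f², df = 2 and N − 3.
- N = 72: lambda = 72 × 0.0961 = 6.92, power **0.630**; chance of a miss 1 − 0.63 = 0.37.
- N = 102: 0.794. N = 105: 0.807. So 0.80 needs **105** infants (35 per group).
- With N = 72, power 0.80 requires f = **0.374**.
- Kruskal-Wallis under normality: about 0.61 (0.608 with relative efficiency 0.955; 0.615 by simulation).

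Power of the one-way ANOVA with N = 72, over f:

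| f | 0.25 | 0.31 | 0.35 | 0.40 |
|---|---|---|---|---|
| Power | 0.44 | 0.63 | 0.74 | 0.85 |

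**3. If a group test on the average of the three scores was meant.** Randomised groups should not differ systematically before the procedure. If the effect is f = 0.31 at the other two times and zero before, the group differences in the average shrink to two thirds: lambda = N·(2f/3)²·3 / (1 + 2·rho).

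| rho | 0.3 | 0.5 | 0.7 |
|---|---|---|---|
| lambda | 5.77 | 4.61 | 3.84 |
| Power | 0.55 | 0.45 | 0.39 |

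If 0.31 is instead the f of the three-score average itself, that test has lambda = 6.92 and power 0.63.

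**4. If both the during and after scores are tested at 0.05.** By simulation (40,000 runs, f = 0.31 at both times), the chance of at least one significant result is 0.82, 0.79 and 0.76 for rho 0.3, 0.5 and 0.7. With no effect at either time, the chance is about 9%. This does not amount to 0.80 power at a 0.05 error rate.

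**The case against.** **The plan contains no arithmetic error.** This stands: 72 is right for its likely inputs. The fault is that the test that was powered and the test that is planned differ.

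**The ANOVA for repeated results could be a mixed ANOVA with a group factor**, which would match a calculation with three groups and three measurements. The sentence is loose enough to allow this, and Friedman applies only when data are non-normal. But Friedman has no group factor, and the plan then assigns intergroup analyses to a separate test. If the group effect in a mixed ANOVA was nonetheless intended, step 3 shows that it falls short once the groups are equal before the procedure.

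**The meaning of 0.31 is unknown.** This stands as a limit. Under the interaction route, 0.31 would be an interaction effect size, and the single-time-point f could be larger or smaller; 72 would suffice from about f = 0.374. So 0.63, 105 and 37% are conditional. That one-way ANOVA with 72 infants has 0.63 power at f = 0.31 is true whichever route produced 72.

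**The 0.63 is for the three-group omnibus test, whereas the hypotheses compare each intervention with control.** Fair, but the pairwise figures do not rescue 0.80. If both interventions differ equally from control, d = 0.31 × 3/√2 = 0.66, and an unadjusted two-sample t-test with 24 per group has power 0.61. With evenly spaced means, the extreme pair has 0.73 and an adjacent pair 0.25.

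**Seventy-two is a minimum.** True, but the plan commits to no larger number.

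**Conclusion.** The concern holds. The 0.80 belongs to a calculation that counts three measurements per infant, while the between-group test named in the plan uses one. If f = 0.31 for a single measurement, power at one time point is 0.63 (about 0.61 for Kruskal-Wallis), and the chance of missing the planned effect there is about 37% rather than 20%. Two elements are inferred: that the one-way test is applied at a single time point, and which G*Power procedure gave 72. The mismatch does not depend on which of the two routes was used. The exact size does depend on what 0.31 means, with power from 0.44 at f = 0.25 to 0.85 at f = 0.40. The power statement should be corrected before results are interpreted against it.

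**What to change.** **Required.** Restate the power for the planned test, for example: with 24 infants per group, one-way ANOVA at a single time point has 0.63 power for f = 0.31 and 0.80 power for f = 0.374, at alpha 0.05.

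**To complete the record.** Name the G*Power procedure, correlation and non-sphericity value that gave 72, and state whether 0.31 is Cohen's f for one measurement.

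**Optional.** An analysis that uses the repeated scores could recover power: an ANCOVA of the mean of the during and after NIPS scores, adjusted for the before score. With f = 0.31 at both later times, a during–after correlation of 0.5 and unit variance, the residual variance is 0.75 − r², where r is the correlation of the before score with each later score. Then lambda = 72 × 0.0961 / (0.75 − r²), df 2 and 68. Power is 0.91 for r = 0.5, 0.82 for r = 0.3 and 0.76 for r = 0. These correlations are assumptions, so the power should be quoted as a range.

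**Cost.** The required change is one or two sentences with no extra infants; the only price is a lower stated power.

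### The N=72 calculation credits the group effect to a pain reading taken before the procedure, so the stated 80% power holds only if f=0.31 already averages in a null baseline

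*Combined protocol and SAP*

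**What the plan says.** Under Study Population and Sample, "the effect size was taken as 0.31 based on" a cited doctoral thesis, "the margin of error was taken as 0.05", "the power value was taken as 0.80", and "the number of groups was taken as 3, and the number of measurements was taken as 3". The result follows: "The calculation resulted in a minimum participant number of 72", and so "it was planned to include a minimum of 24 participants in each group". The section gives neither the G*Power test nor the correlation among repeated measures. It does not say whether 0.31 is an effect averaged over the three readings or an effect at a particular reading.

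The timing of the pain readings appears only under Application Tools (Video Camera), where video is used "to determine pain levels before, during, and after the Hepatitis B vaccination procedure in infants". One of the three readings therefore precedes the procedure. The Aim describes "tapping the injection site prior to the second dose of Hepatitis B vaccine" and vibration throughout the procedure. No section says whether the first pain score is taken before tapping or vibration begins.

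Data Analysis plans one-way ANOVA or Kruskal-Wallis between groups, and ANOVA or Friedman for the repeated measurements. It plans no baseline adjustment and names no group effect averaged over time.

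**The concern.** A between-groups test on repeated measures gains power by averaging several readings that all carry the same group effect. A reading taken before any intervention carries none, because randomisation makes its expected difference between arms zero. Including it in the average shrinks the signal by a third and still adds noise.

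Two things are at stake. The 80% may be overstated for the plan's own measurement schedule. And if the sponsor settles the analysis by adopting the three-reading group effect because it fits N=72, the dilution is built into the main pain comparison.

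**Working it through.** **Inputs from the plan.** Three groups, three measurements, f=0.31, alpha 0.05, target power 0.80, N=72 (24 per arm), from Study Population and Sample. Readings before, during and after, from the Video Camera paragraph.

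**Assumed, because not stated.** Between-factors repeated-measures ANOVA, correlation 0.5 unless varied, later SDs equal and set to 1.

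**1. The plan's figure.** The group test is a one-way F test on each infant's mean, with λ = f²N/v, degrees of freedom 2 and N−3, and v = (1+2ρ)/3. At ρ=0.5, v=0.667.
- N=72: λ = 0.0961×72/0.667 = 10.38, power 0.813.
- N=69: power 0.794.

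So 72 is the smallest balanced size that reaches 0.80. Alternatives do not give it: one-way ANOVA needs 105, within factors 21, the group-by-time interaction 24. Between factors needs 57 at ρ=0.3 and 84 at ρ=0.7.

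**2. Null first reading, 0.31 at both later readings.** The effect on the average is 0.31×(0+1+1)/3 = 0.207, so λ = 0.207²×72/v = 3.075/v (unrounded 0.2067). With pre-procedure SD s, correlation r between the pre-procedure and later scores, and 0.5 between the two later scores, v = (s²+3+4rs)/9. The rows for common correlation 0.3 and 0.7 use v = (1+2ρ)/3.

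| Case | v | λ | Power at 72 |
|---|---|---|---|
| Equal SDs, common correlation 0.5 | 0.667 | 4.61 | 0.453 |
| Equal SDs, common correlation 0.3 | 0.533 | 5.77 | 0.547 |
| Equal SDs, common correlation 0.7 | 0.800 | 3.84 | 0.386 |
| s = 0.5, r = 0.5 | 0.472 | 6.51 | 0.60 |
| s = 0.1, r = 0.5 | 0.357 | 8.62 | 0.73 |
| s near 0 | 0.333 | 9.23 | 0.76 |
| s = 1, r = 0 | 0.444 | 6.92 | 0.63 |

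Simulation (20,000 runs) gave 0.457 for the first row and 0.60, 0.73 and 0.76 for the three reduced-SD rows.

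**3. If 0.31 is already the three-reading average.** Power stays 0.813, and the effect during and after must be 0.31×3/2 = 0.465. If both active arms differ equally from control, f = d√2/3, so d is 0.99 SD rather than 0.66 SD.

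**4. Outcomes that leave out the first reading, f=0.31 on the analysed score.** Here λ = 0.0961×72/v = 6.92/v. The covariate takes one degree of freedom (68 instead of 69).

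| Analysed score | v | λ | Power at 72 |
|---|---|---|---|
| During alone | 1 | 6.92 | 0.63 |
| During, covariate, r = 0.2 | 0.96 | 7.21 | 0.65 |
| During, covariate, r = 0.5 | 0.75 | 9.23 | 0.76 |
| Mean of during and after | 0.75 | 9.23 | 0.76 |
| Mean, covariate, r = 0.2 | 0.71 | 9.75 | 0.79 |
| Mean, covariate, r = 0.5 | 0.50 | 13.84 | 0.91 |

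The first row is also the power of the one-way ANOVA named in Data Analysis, applied to a single later reading.

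**5. How far the two-reading mean depends on its assumptions.** If the effect exists only during the procedure, its averaged size is 0.31/2 = 0.155, λ = 0.155²×72/0.75 = 2.31, and power is 0.25. If 0.31 is the three-reading average, λ = 0.465²×72/0.75 = 20.76, and power is 0.98.

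**The case against.** The strongest reply is that nothing is wrong with the arithmetic. In the calculation that reproduces 72, f is by definition the effect on the average, and on that reading 0.81 stands. This is correct, and it is why the conclusion is conditional. But the plan does not say that 0.31 was obtained that way, and if it was, the later effect being assumed is half as large again.

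A second reply is that Data Analysis names no group effect averaged over time, so the diluted test may never be run. That also stands. A reader might infer that the planned group comparison has power 0.45, or that the one-way ANOVA does worse than the three-reading test. The documents support neither: a one-way ANOVA at one later reading is not diluted and has power 0.63. That is still below 0.80 if 0.31 applies to that reading.

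Third, a reader might take 0.45 as the single answer. It needs 0.31 to be the effect during and after, equal SDs, and a common correlation of 0.5. On a 0 to 7 scale, calm infants may vary little before the needle, which moves the figure towards 0.60 to 0.76.

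Fourth, that the arms cannot differ at the first reading is not established. Tapping comes before the injection, and the order of tapping and scoring is not given. If scoring follows tapping, the reading is not a baseline and cannot be used as a covariate. Its timing needs stating either way.

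**Conclusion.** The point holds in conditional form. The sample size fits a test that counts three readings as carrying the group effect, while the measurement schedule places one before the procedure. If that reading precedes any intervention, and unless 0.31 already averages in a null baseline, the 80% is not delivered at the correlation that reproduces 72. Power of the three-reading group effect is about 0.45 with equal SDs and common correlation 0.5, 0.60 to 0.76 with a pre-procedure SD of half the later SD or less, and 0.63 if the first score is uncorrelated with the later ones. If 0.31 is such an average, 0.81 stands with a later effect of 0.465.

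The test and the correlation are inferred from the match to 72. The SDs and the meaning of 0.31 are not given and cannot be settled from the documents. For the same reason no single replacement figure can be prescribed: a reader might infer that the corrected power is 0.76, but that holds only if 0.31 applies to the mean of during and after at correlation 0.5. The documents do not show that the trial needs more infants.

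**What to change.** **Data Analysis.** Compare arms on one pre-specified post-baseline pain score. The score during the procedure matches the hypotheses. The mean of during and after is an alternative if the sponsor expects the effect to persist. Keep the pre-procedure score out of the outcome and enter it as a baseline covariate, provided it is scored before any tapping or vibration. State that timing.

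**Study Population and Sample.** Name the test, the correlation and what f=0.31 refers to, and restate the power at N=72 for the chosen analysis. With 0.31 on the analysed score, this is 0.63 for during alone (0.65 to 0.76 with the covariate at correlation 0.2 to 0.5 with the later score). For the mean of during and after at correlation 0.5 it is 0.76 (0.79 to 0.91 with the covariate).

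**Cost.** A recalculated figure, a few sentences, one covariate degree of freedom and possibly a lower stated power. No more infants are needed. The choice of score should be fixed before data are seen, so that the reading cannot be selected by its result.

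### Video scoring of pain and crying is planned, but no scorer is said to be unaware of the arm, and crying time is recorded on a form that carries the group

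*Combined protocol and SAP*

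**What the plan says.** - **Newborn Baby Observation Form (Data Collection Tools).** The form holds "the baby's group, crying time with the start of the vaccination procedure" and physiological readings. This information "will be observed by the researcher and recorded on this form". NIPS is not among the listed items.
- **Video Camera (Application Tools).** A phone camera is planned "to determine pain levels before, during, and after the Hepatitis B vaccination procedure in infants", for physiological parameters, and "to accurately calculate crying times, and to check for inter-observer agreement in the evaluation of pain scores". The section does not say who scores the video, whether the video crying time replaces the form entry, or what the scorer knows about the arm.
- **NIPS.** Six behaviours are judged. The items include leg movements and crying: "leg movements, and alertness are scored as 0 or 1, while crying is scored as 0, 1, or 2". No rater is named.
- **Aim.** One intervention is "tapping the injection site prior to the second dose of Hepatitis B vaccine". The other is "application of mechanical vibration to the injection site throughout the vaccination procedure".
- **Research Hypotheses.** Both main hypotheses concern pain, and each compares one method with routine vaccination. The tapping hypotheses place the tap during vaccination, whereas the Aim places it before.
- **Type of Research and Data Analysis.** The design is a randomised controlled trial with no masking term attached. Groups are compared by one-way ANOVA or Kruskal-Wallis. Neither section mentions masking.

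**The concern.** Pain is the subject of both main hypotheses, and NIPS is the only pain scale described. Every NIPS item is an observer's judgement. Crying time is less open to interpretation, but someone still decides when crying starts and stops. A scorer who knows or sees the arm may score the study arms lower without meaning to, and the analysis cannot separate that from a real effect.

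The agreement check does not protect against this. It measures whether two observers give the same score, and two observers who both know the arm can give the same biased score. A judgement made with knowledge of the arm cannot be made masked afterwards, so the matter is best settled before data collection.

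**Working it through.** **1. What the text settles**

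| Question | Crying time | NIPS |
|---|---|---|
| Source | Researcher's form entry, and also video | Video, by the camera sentence |
| Value analysed if both exist | Not stated | Not stated |
| Scorer | Researcher for the form; not stated for video | Not stated |
| Scorer unaware of the arm | Not stated; the form carries the group | Not stated |

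The background, methods, tools and analysis sections contain no statement of blinding, masking or an independent assessor.

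**2. The plan's own figure**

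The stated minimum is 72 (24 per group), from f = 0.31, alpha 0.05, power 0.80, 3 groups and 3 measurements. It reproduces as a between-factors repeated-measures ANOVA with lambda = f² × N × m / (1 + (m − 1) × rho), taking rho = 0.5 (assumed; the plan gives none). At N = 72, lambda = 0.0961 × 72 × 3 / 2 = 10.38 and power is 0.813. The smallest N is 70, or 72 with equal groups. The masking point does not depend on this figure; it only fixes 24 per arm.

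**3. Illustration: what an assumed shift would do**

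The plan gives no bias size and no SD, so both are assumed. Take no true effect and a shift of d SD in both study arms, (0, d, d). For the one-way ANOVA, lambda = 24 × sum of (shift − mean shift)² = 24 × (4/9 + 1/9 + 1/9) × d² = 16d², with F on (2, 69) degrees of freedom.

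| d | lambda | ANOVA significant | Kruskal-Wallis (20,000 simulated trials) |
|---|---|---|---|
| 0 | 0 | 5% | 4.8% |
| 0.1 | 0.16 | 6.2% | 6.1% |
| 0.25 | 1.00 | 12.9% | 12.4% |
| 0.5 | 4.00 | 40.0% | 38.3% |

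A second simulation treats NIPS as a whole number from 0 to 7 (assumed latent mean 4 or 5.5, latent SD 1 to 2, 4,000 trials per case). A random fraction of study-arm infants is scored one point too low.

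| Fraction | ANOVA | Kruskal-Wallis |
|---|---|---|
| None | 4.4% to 5.0% across both tests | (same range) |
| One in four | 7% to 13% | 7% to 12% |
| One in two | 13% to 35% | 12% to 33% |

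**4. What masking could and could not remove**

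Suppose masking removes the shift for tapping only. In the order control, vibration, tapping, the pattern becomes (0, d, 0). Pairwise figures are for a two-sided t test, 24 against 24, with noncentrality d × √12.

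| Comparison | d = 0.25, before | after | d = 0.5, before | after |
|---|---|---|---|---|
| Tapping vs control | 13.6% | 5% | 39.6% | 5% |
| Vibration vs control | 13.6% | 13.6% | 39.6% | 39.6% |
| Vibration vs tapping | 5% | 13.6% | 5% | 39.6% |
| Three-group ANOVA | 12.9% | 12.9% | 40.0% | 40.0% |

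The ANOVA row does not change because (0, d, 0) also gives lambda = 16d². Partial masking thus cleans the tapping comparison, does nothing for the three-group test, and brings bias into vibration versus tapping.

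**The case against.** **NIPS may already come from video.** This largely stands. A reader might infer that an unmasked researcher will score NIPS at the bedside. The documents do not support that: NIPS is not on the observation form, no rater is named, and the phrase "is objectively assessed at the bedside" describes the scale in general, not this trial's procedure. The camera sentence is the trial-specific statement, and it points to video. What is missing is any statement that the video scorer is unaware of the arm.

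**A group field on a form does not show that a scorer saw it.** This is true for NIPS. For crying time the same researcher observes and records on that form, so the point is stronger there, although crying time is the less subjective outcome.

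**Masking cannot be complete.** This is correct for vibration, which can be seen and may be heard. It limits the remedy but does not remove the case for concealing what can be concealed.

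**Cutting clips can create a bias of its own.** This also stands. Starting every later clip and the crying clock at needle insertion would drop distress set off by tapping or device contact, which only the study arms can have. That would favour the interventions.

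**The second observer is inferred.** An agreement check implies more than one observer, but nothing says that any of them is independent of delivery. This person has to be arranged, not assumed.

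**The error rates are assumptions.** They are. No document supports a shift of 0.5 SD or half of the infants being scored too low.

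**Conclusion.** The gap is real: no scorer of NIPS or crying time is said to be unaware of the arm, the agreement check does not make up for that, and crying time is entered by the researcher on a form that shows the group. It should be corrected before data collection.

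The size of any bias is unknown. The rates of 6%, 13% and 40% at 0.1, 0.25 and 0.5 SD show only that a moderate shift would matter at 24 per arm. They rest on assumed shifts, an assumed equal effect on both study arms and no true effect.

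Two stronger readings should be resisted. A reader might infer that the results will be biased by a known amount; nothing in the documents supports that. A reader might also infer that the plan chooses unmasked scoring; it is silent, which is different. An opening section was not available here, so a masking label in that section cannot be excluded. The sections where procedures would be set out contain none.

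**What to change.** 1. State that the analysed NIPS and crying time are the video values.
2. Have them scored by the second observer whom the agreement check implies. That person should not have delivered the intervention or completed the form. Clips should have coded names, come in random order and carry no group label.
3. Record the group separately from the outcome values.
4. For NIPS, use clips that do not show the tapping where the scoring time point allows. Keep the leg in view and the sound on, because the scale needs both.
5. For crying time, reconcile the start point on the Observation Form with the timing of tapping in the Aim (before the dose) and in the tapping hypotheses (during vaccination). Apply one start point in all arms. Also report any crying between first contact and needle insertion, so that distress caused by the intervention is not lost.
6. Report each intervention against control, as the hypotheses ask, alongside the planned three-group test.

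**Cost.** Protocol wording, clip preparation, an independent observer's time and added pairwise reporting. The camera is already planned, and no procedure is added for the infant.

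**Limits to state in the plan.** Vibration is only partly masked. If masking works for tapping only, the three-group test and vibration versus tapping can still carry bias. If the second observer is not independent of delivery, the masking is weaker and this should be reported.
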